## Study Protocol

### Participants

A total of  $N = 58$  Mexican students in grades 1-5 across eight public elementary schools in Sinaloa, Mexico participated in the current study ( $M = 7.25$  students/school, range = 6-8). For each student, one parent and one teacher were designated as “primary” (meaning they would participate in CLS-FUERTE and implement the strategies) and asked to complete all measures. All data was collected at the students’ respective schools. See Table 2 for demographic information and Figure 1 for participant flow.

**Recruitment.** Recruitment occurred between May and September each year and began with invitations to school principals suggested by the local SEP. As described in the introduction, as part of our augmented outreach/recruitment plan for Mexico, we invited all families and personnel in participating schools to an informational gathering in September in which we showed a silent video depicting a child with attention and impulse-control difficulties (i.e., the Behavioral Impairment Video; Haack, Gerdes, Lawton, & Schneider, 2014). We encouraged families to contact us if interested in a program to help children similar to the child in the video. School personnel also identified candidate children and contacted families about participating. See Figure 1 for recruitment flow and number of students deemed ineligible at each step of recruitment.

**Screening.** Interested parents scheduled an appointment to screen for eligibility. If parents attended the screening appointment, reported willingness/ability to participate in sessions, and described at least six youth symptoms of inattention and/or hyperactivity with at least one area of related impairment (i.e., school, family, or social impairment), we scheduled meetings for baseline assessments.

**Baseline Assessment.** After completing informed consent procedures approved by UCSF Committee on Human Research, parents and teachers of successfully screened students completed questionnaires, including the Child Symptom Inventory (CSI-4; Gadow & Sprafkin, 1997), Impairment Rating Scale (IRS; Fabiano et al., 2006), and demographic/history form. Students meeting the following criteria were eligible to participate: (a) at least six CSI-4 inattention symptoms and/or six

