hyperactive/impulsive symptoms endorsed by parent or teacher as occurring often or very often, (b) at least one area of IRS functioning rated as  $\geq 3$  by both parent and teacher, thereby indicating cross-setting impairment, (c) a parent available to participate; and (d) a primary teacher agreeing to participate. The assessment and screening algorithm based on at least six symptoms per domain reported by parents or teachers has been used in previous school-based ADHD trials (Haack et al., 2018; Pfiffner et al., 2016) and is associated with strong predictive validity for ADHD (sensitivity = .80, specificity = .58; Gadow & Sprafkin, 2002) and ODD (sensitivity = .70, specificity = .90; Gadow & Sprafkin, 2002) diagnoses. Students taking medication were eligible as long as regimens were stable. Students with significant visual or hearing impairments, severe language delay, psychosis, or pervasive developmental disorder or who were in full-day special classrooms were excluded. Eligible students provided assent before participating.

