### **Data Analytic Approach**

We performed all statistical analyses using SPSS (Version 26; IBM Corp, 2019). We analyzed outcomes in three domains (i.e., ADHD and ODD symptoms, and overall impairment) separately for each rater (i.e., parent and teacher). Primary analyses involved generalized estimating equations (GEE) using the SPSS GENLIN procedure with unstructured correlation matrices to examine within (baseline; post-treatment) and between (CLS-FUERTE vs BAU) group comparisons, adjusting for school clustering. GEE was chosen over alternative methods due to relaxed distribution requirements. Analyses were completed initially without covariates. We then performed follow-up analyses adjusting for parental level of education and child age, gender, and ADHD medication status; however, inclusion did not change the pattern or interpretation of results. Therefore, simple analyses without covariates are presented. To control

for Type 1 Error, a Benjamini-Hochberg false discovery rate (FDR; Benjamini & Hochberg, 1995) was applied within domain. The FDR exerts a more powerful control over wrongly rejecting the null compared to other procedures that control for family-wise error (e.g., Bonferroni correction). For all pairwise comparisons, Hedges'  $g$  effect size metrics are provided. Hedges'  $g$  estimates are Cohen's  $d$  estimates corrected for the upward bias associated with smaller sample sizes. Interpretation of Hedges'  $g$  estimates are consistent with traditional effect size conventions (i.e., 0.2 = small; 0.5 = moderate; 0.8 = large).

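### Within-arm baseline-to-post comparisons are primary beside the randomized comparison, and no group-by-time contrast is named as the efficacy test

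*Combined protocol and SAP*

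**What the plan says.** The Data Analytic Approach has one sentence on the primary analysis. It describes GEE models fitted "to examine within (baseline; post-treatment) and between (CLS-FUERTE vs BAU) group comparisons", adjusted for school clustering. Outcomes are analysed "in three domains (i.e., ADHD and ODD symptoms, and overall impairment) separately for each rater", which gives 3 domains x 2 raters = 6 outcomes. A Benjamini-Hochberg correction "was applied within domain"; neither its level q nor the tests in each family are given. Hedges' g is reported "For all pairwise comparisons", with no split between within-arm and between-arm comparisons. The section names no group-by-time interaction, difference in change or post-treatment difference as the efficacy test.

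The Participants section describes selection on high scores:

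- At screening, parents had to have "described at least six youth symptoms of inattention and/or hyperactivity".
- At baseline, the CSI-4 criterion was a count of six or more in either symptom group (inattention, or hyperactivity and impulsivity), where a symptom counted if it was "endorsed by parent or teacher as occurring often or very often".
- The impairment criterion requires "at least one area of IRS functioning rated as" 3 or more by both the parent and the teacher.
- ODD symptoms are not an entry criterion.

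**The concern.** A within-arm change from baseline does not compare randomized groups. It combines any treatment effect with everything else that moves scores between September and December, including regression to the mean after selection on high ratings. That selection acts directly on two of the three outcome domains, ADHD symptoms and overall impairment. A fall within CLS-FUERTE in those domains cannot show that the programme worked.

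The between-arm contrast does not share this weakness. Students in both arms met the same entry criteria, baseline assessments came before randomization (Study Design), and post assessments took place at the same time in both conditions (BAU Condition).

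Two things are at stake. First, with both kinds of comparison labelled primary, nothing in the plan stops a result of the form *significant in CLS-FUERTE, not significant in BAU* from being presented as a primary finding of benefit. Second, because the correction families are not listed, a reader cannot tell what threshold the randomized comparison had to meet.

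**Working it through.** The documents give no alpha, power, effect size or q, so there is no stated figure to reproduce. Two consequences can be sized.

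**1. Reading within-arm significance as efficacy**

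Inputs:

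- 28 CLS-FUERTE and 31 BAU students (Study Design). These sum to 59, while Participants gives 58; using 28 and 30 moves the results below by less than one percentage point.
- Assumed: two-sided 5% tests, and the same mean improvement *d* in both arms, in units of the SD of change. There is then no treatment effect.
- Clustering is ignored and the arms are treated as independent.

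Formula: the chance of a significant within-arm improvement is Φ(d√n − 1.96). The chance that CLS-FUERTE is significant and BAU is not is P(CLS) x [1 − P(BAU)].

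For d = 0.3: Φ(0.3 x √28 − 1.96) = Φ(−0.373) = .355, and Φ(0.3 x √31 − 1.96) = Φ(−0.290) = .386. The product is .355 x .614 = .218.

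| d | CLS-FUERTE significant | BAU significant | CLS-FUERTE significant, BAU not |
|---|---|---|---|
| 0.2 | .184 | .199 | .147 |
| 0.3 | .355 | .386 | .218 |
| 0.4 | .562 | .605 | .222 |
| 0.5 | .754 | .795 | .154 |
| 0.6 | .888 | .916 | .074 |

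The misleading pattern therefore arises in about 7% to 22% of outcomes at these five values. Between grid points it peaks slightly higher: at d = 0.35, .457 x .505 = .231. With no change in either arm it would be .025 x .975 = .024. The last two columns are only part of the problem: at d = 0.6, CLS-FUERTE alone shows a significant fall 89% of the time with no treatment effect.

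**2. The threshold for the randomized test if within-arm tests share a family**

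Assumed: q = .05. The alternatives compared are a two-test family (between-arm, parent and teacher) and a six-test family that adds four within-arm tests (2 arms x 2 raters). The larger between-arm p-value is taken as clearly non-significant. Of the four within-arm tests, k have very small p-values and the rest are clearly non-significant.

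- Two-test family: the cut-off for the smaller between-arm p-value is 1/2 x .05 = .025.
- Six-test family: that p-value has rank k + 1, so its cut-off is (k + 1)/6 x .05.

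| k | Six-test cut-off |
|---|---|
| 0 | .0083 |
| 1 | .0167 |
| 2 | .0250 |
| 3 | .0333 |
| 4 | .0417 |

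With between-arm p-values of .02 and .30, the .02 is rejected in the two-test family, but in the six-test family only when k is at least 2. With .03 and .30, nothing is rejected in the two-test family, but the .03 is rejected in the six-test family when k is at least 3. Pooling can thus remove or create a between-arm finding, depending on tests that carry no information on efficacy.

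**The case against.** Pairing within and between is common shorthand for the time and group factors of a single GEE. Study Design declares a cluster randomized comparison of CLS-FUERTE with BAU, and nowhere do the documents claim efficacy from within-arm change. This is fair as a possible reading, but it does not settle the point: the text speaks of group comparisons, refers to all pairwise comparisons, and never names the interaction. Even on that reading the efficacy contrast remains unnamed, and the remedy is the same.

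A reader might go further and infer that within-arm tests were pooled into the correction and inflated false positives. The documents do not support this. They do not say that the tests were pooled, and parent plus teacher is a natural reading of a family formed within a domain. The six-test family and q = .05 are assumptions, and other family sizes are possible. Nor would pooling necessarily be liberal. With assumed regression-to-the-mean effects in ADHD and impairment, simulated chances of any false between-arm finding over three domains were 7% to 13% with shared families, against 9% to 14% with between-arm families only. A rise from about 14% to about 23% appears only in the extreme case where essentially every within-arm test rejects and the domains are independent.

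The size of the common change is also not in the documents. A simple selection model gave within-arm rejection rates of 8% to 43% for ADHD and 20% to 94% for impairment. That spread depends on assumed cut-offs, retest and rater correlations, and on outcomes being scored like the eligibility ratings, which the text does not state. It is too wide to narrow the 0.2 to 0.6 range.

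**Conclusion.** The point holds as a defect in a stated primary analysis: within-arm comparisons are given primary status, and the randomized difference in change is not named as the efficacy test. Selection on raised ratings makes within-arm falls in ADHD symptoms and impairment unsafe as evidence of benefit. The argument does not carry over directly to ODD, and it does not imply bias in the between-arm contrast.

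The misleading within-arm pattern has a chance of about 7% to 22% per outcome under equal changes of 0.2 to 0.6 SD, two-sided 5% tests and no allowance for clustering. This figure needs no assumption about the correction families.

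The family question is an omission with an unknown consequence. If pooling occurred, the cut-off for the smaller between-arm p-value could lie anywhere from .0083 to .0417 instead of .025, given q = .05 and the family sizes assumed. It would be wrong to conclude that pooling happened or that false positives were inflated. The change is worth making because it concerns the primary claim and costs little.

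**What to change.** - Name the group-by-time contrast from the existing GEE as the only efficacy test for each domain and rater.
- Apply Benjamini-Hochberg within each domain to the two between-arm tests (parent, teacher), at a stated q.
- Label within-arm changes as secondary and descriptive, outside the correction families and not used to claim efficacy. Their p-values need not be removed.
- If *within* meant only the time factor of one model, say so; the designation above still applies.
- The section is written in the past tense and already reports that covariates did not alter the results, so state that this designation was made after the analyses were run.

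Cost: rewording, and re-running the correction on two p-values per domain. The downsides are that within-arm results lose primary status and that the between-arm threshold may shift slightly if the families were formed differently. If the analysis was already done this way, a short clarification of the contrast, the family members and q is enough.

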### **Study Design**

A 2-level (students, schools) cluster RCT design (Hayes & Moulton, 2009) accounted for treatment (CLS-FUERTE or BAU) within level 2 (schools). We randomized schools to CLS-FUERTE (school n = 4, student n = 28) or BAU (school n = 4, student n = 31). We determined our sample size based on practical considerations (i.e., previous CLS trial experience, years of funding). Each year, schools were divided into high or low Socioeconomic Status (SES) categories (determined by the Secretary of Public Education; SEP) after baseline assessments were completed in September. The first author coded schools to conceal their identity until treatment was assigned and a statistician randomized concealed ordered pairs to CLS-FUERTE or BAU using a random number generator. Those randomized to CLS-FUERTE received the intervention between October and December, followed by post assessments for all families in December each year.

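### Eight schools were randomized, four per arm, but the primary between-arm GEE states no inference suited to eight clusters, so its p-values are probably too small

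*Combined protocol and SAP*

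**What the plan says.** The Participants section places the students "across eight public elementary schools in Sinaloa, Mexico". The Study Design section describes a two-level cluster trial that "accounted for treatment (CLS-FUERTE or BAU) within level 2 (schools") and reports the allocation: "We randomized schools to CLS-FUERTE (school n = 4, student n = 28) or BAU (school n = 4, student n = 31"). Each year, schools were grouped by socioeconomic status after baseline, and then "a statistician randomized concealed ordered pairs to CLS-FUERTE or BAU using a random number generator".

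The Data Analytic Approach names GEE fitted with the "SPSS GENLIN procedure with unstructured correlation matrices", covering within-group and between-group comparisons; the latter are described as "group comparisons, adjusting for school clustering". The only reason given for the method is that "GEE was chosen over alternative methods due to relaxed distribution requirements". Three domains are each analysed for two raters, so there are six outcomes, and a Benjamini-Hochberg correction "was applied within domain".

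The section does not give the GENLIN subject variable, the variance estimator, the reference distribution or degrees of freedom, alpha, the exact between-arm contrast (change from baseline or post-treatment level), or how the randomized pairs enter the analysis. Its one small-sample correction applies to the effect size, Hedges' g.

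**The concern.** Treatment varies only between schools, so the between-arm comparison rests on eight independent units. The usual GEE robust variance and its normal or chi-square Wald test are justified by a large number of clusters. With four per arm, the variance is biased downwards and the reference distribution has tails that are too light. Relaxed distributional assumptions do not help with either problem.

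The two phrases that describe the model also pull apart. An unstructured matrix fits naturally with the student as subject, measured twice. Adjustment for school clustering suggests the school as subject. A reader cannot tell which model was run, and neither reading is reliably valid with an uncorrected Wald test.

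At stake are the between-arm p-values for all six rater-by-domain outcomes. A false discovery rate procedure takes its input p-values as valid, so it passes any error on. The within-group comparisons are outside this point.

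**Working it through.** The plan has no power, alpha or sample-size calculation to reproduce; the sample size was set on practical grounds.

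**Inputs from the documents.** 4 v 4 schools; 6 to 8 students per school, mean 7.25; two time points. (The arm totals give 28 + 31 = 59 students against a stated N of 58. This does not affect the result.)

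**Assumed.** Two-sided 5%; an uncorrected sandwich with a normal or chi-square Wald test; change from baseline as the contrast; ordered pairs read as matched pairs of schools. The documents give no ICC and no pair correlation, so ranges are shown.

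**1. Can the stated matrix be fitted?**
- School as subject: 6 to 8 students measured twice is 12 to 16 measurements per school. An unstructured matrix has 12 × 11 / 2 = 66 to 16 × 15 / 2 = 120 correlations. Eight schools cannot estimate these.
- Student as subject: two measurements, so one correlation. This can be estimated, but school is then outside the robust variance.
- Student as subject with school as a model factor: in a difference in change, the school main effect cancels. Fitted GEEs gave the same rejection rates with and without the factor (5.2%, 14.7% and 22.4% at change-score ICC 0, 0.10 and 0.20; 3,000 runs).

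**2. School as subject, independence working correlation.** With m = 4 equal schools per arm, the uncorrected sandwich divides by m rather than m - 1, so it is 6/8 of the unbiased variance. The true rejection rate is

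2 × P(t6 > 1.960 × √(6/8)) = 2 × P(t6 > 1.697) = 0.1405.

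Simulation with school sizes of 6 to 8 and ICC from 0 to 0.20 gave 13.9% to 14.3%, so the figure hardly depends on ICC or on unequal sizes. Fitted two-time-point GEEs gave 14.9% (independence) and 13.5% (exchangeable), with a Monte Carlo SE of 0.9 points.

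**3. Effect of correlation r between paired school means.** Rejection rate under no effect, simulated:

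| r | Uncorrected sandwich, normal | Two-sample t, 6 df | Paired t, 3 df |
|---|---|---|---|
| -0.3 | 19% | 7.8% | 5.0% |
| 0 | 14.1% | 5.0% | 5.0% |
| 0.1 | 12.4% | 4.2% | 5.0% |
| 0.3 | 9.2% | 2.8% | 5.0% |
| 0.5 | 6.0% | 1.6% | 5.0% |
| 0.6 | 4.5% | 1.2% | 5.0% |

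**4. Student as subject.** If the total variance were known, the rate would be 2 × P(Z > 1.960/√D), with D = 1 + (7.25 - 1) × ICC. For ICC 0.05, 0.10 and 0.20, D = 1.3125, 1.625 and 2.25, giving 8.7%, 12.4% and 19.1%. Estimating the variance from the students adds a little: simulation gave about 6%, 10%, 14% and 22% at ICC 0, 0.05, 0.10 and 0.20 without pair correlation. With school effects correlated 0.5 within pairs, the rates were 7.6%, 9.6% and 13.4% at ICC 0.05, 0.10 and 0.20.

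**5. Both corrections are needed.** For school as subject with uncorrelated pairs:
- variance corrected by m/(m - 1), normal reference: 9.8%
- uncorrected variance, t on 6 df: 7.8%
- both corrections: 5.0%.

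**The case against.** The strongest reply is that the plan says it adjusts for school clustering and nowhere says that an uncorrected test was used. That stands in part. A reader might infer that this trial's false-positive rate is 14%, or that its p-values are known to be too small. The documents support neither. The 14% belongs to school as subject with an independence working correlation, which is not the unstructured fit the plan names. Under student as subject with an ICC near 0, the rate is close to nominal. What remains is that no literal reading of the section, combined with an uncorrected Wald test, is reliably valid for eight schools. Adjusting for clustering is not the same as valid inference with few clusters.

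A reader might also infer that pairing can only help. That is true for positive correlation, the direction one would expect from socioeconomic grouping. Negative correlation raises the rate, and the plan does not define the pairs further.

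A third reply is that a t-test on 6 df is partly a preference, since schools were randomized in pairs. This stands. The paired test holds 5% at every correlation in the table, whereas the 6 df test is conservative under positive correlation and too liberal under negative correlation. Against that, the paired test has only 3 df. At the effect that gives the 6 df test 80% power with uncorrelated pairs, the paired test has 62%; at r = 0.5 it has 87% against 84%. Neither test is better throughout.

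Finally, the contrast is not stated. If the between-arm comparison is at post-treatment, a test on school-mean change would answer a different question.

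**Conclusion.** The concern holds, as a conditional one. The documents establish that eight schools were randomized and that the primary between-arm GEE states no inference suited to that number. They also establish that the stated working correlation and the stated school adjustment do not fit together in any model that is plainly valid here.

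The size depends on assumptions the documents cannot settle: which subject variable was used, whether the Wald test was uncorrected, the ICC and the pair correlation. Over the values examined, an uncorrected test at two-sided 5% rejects between about 4.5% and 22% of the time under no effect, and most of these settings lie above nominal. These are illustrations, not bounds. The between-arm p-values are therefore probably too small. Confidence is high about the omission and lower about how far the reported p-values are affected.

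This matters enough to require a change, because it bears on the primary between-arm conclusion for all six outcomes.

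**What to change.** In the Data Analytic Approach:

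- Base the between-arm conclusion for each of the six outcomes on a test valid for eight schools. Use either a two-sample t-test on the eight school means (6 df), or GEE with school as subject, an independence or exchangeable working correlation, and a small-sample-corrected sandwich with t on 6 df. The two are essentially equivalent at these school sizes.
- Report beside it the paired t-test on the randomized pairs (3 df if there are four pairs), and state how the pairs were formed.
- State whether the contrast is change from baseline or post-treatment level, and take school means of that same contrast. State alpha.
- Apply Benjamini-Hochberg within domain to the new p-values.
- State the subject variable, variance estimator and reference distribution of the GEE that was run, and that relaxed distribution requirements do not address the number of clusters.
- Label the re-analysis post hoc. The section already reports that adding covariates left the results unchanged, so prespecification cannot be restored.

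A randomization test is not a practical substitute if there are four pairs: its smallest two-sided p-value is 2/16 = 0.125.

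**Cost.** No new data, one simple test per outcome and a few sentences. Intervals become about (2.447/1.960) × √(8/6) = 1.44 times as wide as with the uncorrected school sandwich, and fewer results may be significant. With uncorrelated pairs, 80% power on 6 df needs 3.37 standard errors, where SE = √((ICC + (1 - ICC)/7.25)/2). For a change contrast, that is about 0.88, 1.01, 1.13 or 1.33 SD of change at an assumed ICC of 0, 0.05, 0.10 or 0.20. The 6 df test is conservative if pairs are positively correlated.

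### On the natural reading of the model, the covariate-adjusted follow-up cannot move the comparison of change between arms, so its agreement does not justify presenting only unadjusted results

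*Combined protocol and SAP*

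**What the plan says.** In the combined protocol and SAP, Data Analytic Approach, the primary analyses use "generalized estimating equations (GEE) using the SPSS GENLIN procedure with unstructured correlation matrices" and are meant "to examine within (baseline; post-treatment) and between (CLS-FUERTE vs BAU) group comparisons, adjusting for school clustering". Baseline and post-treatment scores are therefore both outcomes in one model. The first analyses have no covariates. The section continues: "We then performed follow-up analyses adjusting for parental level of education and child age, gender, and ADHD medication status". It then reports that "inclusion did not change the pattern or interpretation of results. Therefore, simple analyses without covariates are presented". No other reason is given for showing unadjusted results, and adjusted estimates are not promised. The section adds: "For all pairwise comparisons, Hedges' $g$ effect size metrics are provided".

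Two other places matter. Under Participants: "Students taking medication were eligible as long as regimens were stable". Medication status is thus meant to be constant, at least at entry. Under Study Design: "Each year, schools were divided into high or low Socioeconomic Status (SES) categories". That grouping came before randomisation, but the analysis section mentions no SES term.

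The plan does not state the link function, whether covariates entered as main effects only or also crossed with time, the level of the unstructured matrix (student or school), the handling of missing post scores, or whether arm-by-time is the test of interest.

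**The concern.** With four schools per arm, chance imbalance in student characteristics is likely. A reader will take the statement that adjustment made no difference as reassurance on this. It reassures only if adjustment could have made a difference.

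For the comparison of change between arms, the natural version of the follow-up has no way to do so. Unchanged results on that contrast would then be a property of the model, not a finding about the data, and the plan uses them to decide which analysis is shown. An SES main effect added to the same model would be equally inert, because SES category is also constant over a student's two assessments.

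The exposure is limited. A difference in change already removes additive effects of characteristics that do not vary with time. What remains unchecked is imbalance in characteristics that predict how much a child changes.

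**Working it through.** The plan gives no figure to reproduce, so the check is algebra followed by simulation.

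**Algebra.** Let A be arm, t time (0 or 1) and X the student's covariates:

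`Y(t) = b0 + b1*A + b2*t + b3*A*t + g*X + error`

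Subtracting baseline from post gives `Y(1) - Y(0) = b2 + b3*A + error`. X has gone. With complete pairs and an identity link, b3 is the difference in mean change, b2 is the BAU change and b2 + b3 the CLS-FUERTE change. None depends on g. The arm difference at post is b1 + b3; b1 does depend on g, so this contrast can move.

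**Simulation inputs, all assumed except the layout.** 8 schools, 58 students (28 and 30), two times. Standard deviations: school 0.3, school-by-time 0.2, student 0.7, residual 0.5. Arm-by-time effect -0.5. Covariate effects: 0.3 per SD of education, 0.15 per year of age, 0.3 for gender and 0.3 for medication.

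**One illustrative data set, arm-by-time estimate:**

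| Situation | Unadjusted | Adjusted |
|---|---|---|
| Complete data, main effects | -0.3055 | -0.3055 |
| Complete data, covariate-by-time | -0.3055 | -0.2108 |
| 6 of 58 post scores missing, main effects, student-level correlation | -0.295 | -0.277 |
| 6 of 58 missing, main effects, school-exchangeable correlation | -0.363 | -0.285 |

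In the first row the standard error is also identical with and without covariates (0.1854 clustered by student, 0.1836 by school). In the second, the shift is 0.3055 - 0.2108 = 0.0947, or 0.0947/0.1836 = 0.52 standard errors.

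**Sixty data sets, two-by-two unstructured covariance per student, school-level robust standard error:**

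- Main effects, complete data: largest shift 4e-15 in the estimate and 8e-16 in the standard error, which is rounding.
- Main effects, 6 post scores missing: mean absolute shift 0.011, maximum 0.077; significance at 1.96 never changed.
- Covariate-by-time terms, complete data: mean 0.038, maximum 0.117; significance changed in 5%.
- Arm difference at post, main effects, complete data: mean 0.100, maximum 0.341.

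In a further 150 simulated data sets, the mean shift with 6 missing post scores was 0.05 standard errors (maximum 0.17), against 0.20 (maximum 0.87) for covariate-by-time terms on complete data. The size of the shifts depends on the inputs; the exact zero does not.

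**Gain from using baseline as a covariate.** With equal variances and within-student correlation r, ignoring clustering, the variance is proportional to 2(1 - r) for change and to 1 - r^2 for the baseline-adjusted post score. The ratio of standard errors is `sqrt((1 + r)/2)`:

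- r = 0.4: sqrt(0.70) = 0.837, 16% lower
- r = 0.55: sqrt(0.775) = 0.880, 12% lower
- r = 0.7: sqrt(0.85) = 0.922, 8% lower

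Simulations with school clustering (ICC 0.05 to 0.20, r from 0.4 to 0.7, no SES term) gave about 6 to 17%. At ICC 0.10 and r = 0.55, with covariates explaining about 4% of variance, the standard errors were 0.320 (change), 0.280 (baseline-adjusted) and 0.286 (plus the four covariates). The reductions are 1 - 0.280/0.320 = 12.5% and 1 - 0.286/0.320 = 10.6%.

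**Price of the SES term.** Eight schools less two arm means leave 6 degrees of freedom; SES leaves 5. The t critical value rises from 2.45 to 2.57, a factor of 1.049. If SES explained nothing, interval width would be multiplied by between 0.83 x 1.049 = 0.87 and 0.94 x 1.049 = 0.99, so intervals would still be about 1 to 13% narrower.

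**The case against.** A reader might infer that the follow-up could not alter any result and is worthless as a check. The documents do not support that, for three reasons.

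- **The conditions are not stated.** Covariates may have been crossed with time, or some post scores may be missing. Completeness cannot be confirmed: Study Design gives 28 + 31 = 59 students and Participants gives 58. With missing post scores the exact invariance fails. The shift is small on average under a student-level matrix, but reached 0.363 - 0.285 = 0.078 in the school-exchangeable example, about 0.40 of its standard error of 0.195.
- **The matrix may have been set at school level.** Eight schools cannot freely estimate an unstructured matrix of that size. With one shrunk 90% towards independence, the arm-by-time estimate moved by 0.012 on average (maximum 0.042) even with complete data.
- **Arm-by-time is not named as the test.** The plan reports effect sizes for all pairwise comparisons, and the arm difference at post does respond to adjustment. For that contrast the unchanged pattern is evidence.

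Two further inferences also go too far. Eight coefficients against eight schools give a school-clustered robust covariance matrix of rank 7; this blocks a joint test of all coefficients but not a standard error for one contrast. And the text reports completed analyses, so making a new model primary now would replace the primary analysis after results were seen. The plan also gives a reason for choosing GEE, its weaker distributional requirements.

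All of this stands and limits the point. It does not restore the plan's reasoning for the change comparison under the natural reading.

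**Conclusion.** The point holds conditionally. With time-constant covariates as main effects, an identity link, complete pairs and a student-level or exchangeable correlation, agreement on arm-by-time and on the within-arm changes is automatic. It is not evidence of robustness to covariates that predict change. With a few missing post scores the check remains weak on average. For the arm difference at post, the follow-up carries some information.

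Nothing here shows that a trial result is wrong or that a better adjusted analysis would disagree. The defect is that agreement serves as the reason for withholding adjusted estimates when, for one main contrast, it was probably guaranteed. The 6 to 17% gain in standard error is a separate benefit of the remedy and rests on the assumed correlations and ICCs.

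**What to change.** 1. State the model terms, link, level of the working correlation, numbers with both scores, and handling of missing data.
2. Add an adjusted analysis, labelled post hoc, in which covariates can act: post score on arm, with the baseline score of the same measure and rater and the SES category used at randomisation as covariates. Account for school clustering and base inference on eight schools, for example by a REML mixed model with small-sample degrees of freedom.
3. Repeat that model with parental education, age, gender and medication status. If the GEE is kept for this purpose, enter each covariate and SES as a covariate-by-time term.
4. Report adjusted and unadjusted estimates with intervals whether or not they agree, and remove the rule that agreement decides which is presented.

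The existing GEE stays as the primary analysis. The cost is re-running models on data already collected, one extra table and one school-level degree of freedom for SES.
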